**1. PROJECT TITLE**

Neurofeedback-EEG-VR (NEVR) System for Non-opioid Pain Therapy

**4. ESTIMATED DURATION OF THE STUDY**

The entire duration of the study will be for 12 months.

**5. LAY LANGUAGE SUMMARY OR SYNOPSIS (no more than one paragraph)**

This project will investigate an innovative, non-invasive, non-pharmacological pain treatment concept. There is evidence that Virtual Reality usage can assist with acute pain management. In addition, there is evidence that EEG-based neurofeedback (NF), which is training people to control their brainwaves, has the ability to reduce chronic pain perception. Therefore, we will investigate whether a system combining these two methodologies has the potential to assist with both acute and chronic pain management. We call this system Nf +Eeg+VR=NEVR.

**6. SPECIFIC AIMS**

**Aim 1: Validate NEVR on patients with FBSS:** 20 chronic back pain patients will be recruited at UCSD and undergo 20 sessions of NF training with the NEVR prototype. Their pain impact will be assessed through an extensive cognitive and functional battery before and after the first and last NF sessions, along with feedback surveys.

**Aim 2: Define the system specifications and design the Phase II system:** QUASAR will analyze the collected EEG data to determine the minimal subset of electrodes that would be necessary to reliably measure alpha activity in this population. QUASAR will then review the user feedback and develop system specifications and a concept design for a new headset to be built under Phase II.

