## 9. RESEARCH DESIGN AND METHODS

This will be a single arm clinical trial with up to 25 subjects undergoing NF training in VR using the NEVR prototype and protocol. This is a feasibility study where only one arm (NF group) is needed for demonstration of feasibility; the number of subjects is based on a recently published study by Mayaud et al. 2019.

Each patient will be recruited from [name] patient population, and after signing informed consent will undergo a cognitive and behavioral pain assessment followed by 20 NF sessions, every other day or 3 times per week. Each session will take up to 1 hour and will consist of: donning of NEVR system, recording EEG while subjects sit with their Eyes Open then Eyes Closed for EEG threshold calibration, followed by performing six 5-minute blocks of NF. Subjects will then be asked to conduct a brief usability survey after each session. At the end of the 20 sessions, subjects will undergo the same cognitive and behavioral assessment conducted at the study's onset.

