### **Pain Assessments:**

Pain assessment will be conducted prior to and after the first, 10th and last sessions via all of the following battery of standardized subjective, objective, behavioral and functional evaluation tests:

2) Numerical Rating Scale (NRS, or Visual Analog Pain Score (VAS);

Pain scores are measured using a visual analog scale. This consists of a 10 cm line with "no pain" written at one end and the "worst imaginable pain" written at the other end. The patient is asked to place a mark along the line that corresponds with their pain. The distance, in cm, from the no pain end to the location of the mark gives a measurement of the pain. Subjects will be asked to rate their spontaneous pain and evoked pain to movement.

4) The DALLAS scale;

A self-reported disability scale for patients with low back pain assessing the impact on everyday quality of life: work and leisure, anxiety, depression, and sociability; each subpart varies from zero to one hundred percent.

12) Patient Assessment Global Change; and

The patient assessment global change is a 2-item measure assessing individuals perceived improvement following treatment.

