### **Statistical Analyses:**

**EEG:** QUASAR will analyze the EEG data to track changes in alpha activity over the course of the treatment and correlate those to the clinical outcomes. Change in Alpha activity will be calculated between the first and last EEG recordings after the 20 sessions. Furthermore, QUASAR will review the data to determine the minimal subset of electrode locations that would yield reliable detection of alpha activity needed for this NF protocol.

**Behavioral and Cognitive outcomes:** QUASAR will conduct statistical analysis of the results of the pain assessments conducted prior to and after treatment with paired t-test or Wilcoxon signed-rank tests to determine the effects of the treatment (both across the first and last sessions and across the entire 20 sessions). In addition, QUASAR will correlate the clinical outcome measures to the EEG results using cross-correlation analyses and Wilcoxon signed-rank test and will account for multiple comparisons according to the methods described in Mayaud et al, 2019.

**Questionnaires:** Usability survey results will be tabulated and analyzed by QUASAR to inform the design of

the Phase II device.

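### The assessment schedule is described three ways, the pre/post contrast is not defined, and session 10 has no stated use in an analysis that needs a last-session value

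*Combined protocol and SAP*

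**What the plan says.** Three places describe when the pain battery is given.

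- Section 6, Aim 1: assessment takes place "before and after the first and last NF sessions".
- Section 9, opening: each patient "will undergo a cognitive and behavioral pain assessment followed by 20 NF sessions", and then "At the end of the 20 sessions, subjects will undergo the same cognitive and behavioral assessment".
- Section 9, Pain Assessments: "Pain assessment will be conducted prior to and after the first, 10th and last sessions".

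The Statistical Analyses text in section 9 compares assessments made before and after treatment using "paired t-test or Wilcoxon signed-rank tests to determine the effects of the treatment", and adds that this is done "both across the first and last sessions and across the entire 20 sessions". It does not mention session 10, a repeated-measures model or a method for missing assessments. The EEG outcome is likewise a two-point change: "Change in Alpha activity will be calculated between the first and last EEG recordings after the 20 sessions".

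Section 10 sets a maximum of 25 subjects and anticipates drop-out of 10–50%. Section 15 says that data gathered up to discontinuation will be analysed unless the subject withdraws consent for this, but it gives no method.

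**The concern.** There are two linked problems.

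First, the effect to be estimated is not fixed. With readings before and after a session at several points in the course, a pre/post change can mean several things. Section 17 allows that subjects may get pain relief during the VR sessions. A reading taken just after a session may therefore mix immediate relief with lasting change, and the choice of pair can alter the result. The planned correlation of clinical change with EEG change inherits the same uncertainty.

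Second, a paired test uses only subjects who have both members of the pair. A subject who completes session 12 and then leaves has up to four scheduled readings, yet adds nothing to a first-to-last test. With drop-out of up to half, this costs precision. If subjects leave because their pain is not improving, or because it has improved, the completers' mean change is also biased. A session-10 reading that is not taken, because staff worked from Aim 1, cannot be recovered later.

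**Working it through.** **The plan's own figure.** The maximum of 25 rests on a published precedent. No alpha, power, effect size or SD is given, so it cannot be reproduced from a power formula. If Aim 1's 20 patients is read as a target for completers (an assumption), the enrolment needed is 20/(1 − d), rounded up: 23 at 10% drop-out, 25 at 20% and 40 at 50%. A cap of 25 therefore keeps 20 completers only up to 20% drop-out.

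**Step 1: the schedules side by side.** Onset is taken as before session 1, and the end as after session 20.

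| Place | Before 1 | After 1 | Before 10 | After 10 | Before 20 | After 20 | Readings |
|---|---|---|---|---|---|---|---|
| Section 6, Aim 1 | yes | yes | – | – | yes | yes | 4 |
| Section 9, opening | yes | – | – | – | – | yes | 2 |
| Section 9, Pain Assessments | yes | yes | yes | yes | yes | yes | 6 |

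**Step 2: possible contrasts.** With k readings there are k(k − 1)/2 pairs: 1 for k = 2, 6 for k = 4 and 15 for k = 6. On the four-reading schedule, 2 × 2 = 4 pairs run from first to last session and 2 are within-session changes. The analysis text does not say which pairs are meant.

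**Step 3: subjects in a first-to-last paired test.** The number is 25 × (1 − d).

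- d = 10%: 25 × 0.90 = 22.5
- d = 50%: 25 × 0.50 = 12.5

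That is about 12 to 22 pairs.

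**Step 4: subjects with a session-10 reading but no last-session reading.** Let s be the share of drop-outs who leave after session 10. The documents do not give s, so the whole range is shown. The number is 25 × d × s.

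| Drop-out | s = 0 | s = 0.5 | s = 1 |
|---|---|---|---|
| 10% | 0 | 1.25 | 2.5 |
| 50% | 0 | 6.25 | 12.5 |

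Adding the completers, the number with a session-10 reading is 22.5, 23.75 or 25 at 10% drop-out, and 12.5, 18.75 or 25 at 50%.

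**Step 5: what the loss of pairs means for precision.** For a paired t-test with an assumed two-sided alpha of 0.05 and 80% power (noncentral t), the detectable standardized change is 0.63 at n = 22, 0.66 at n = 20 and 0.89 at n = 12. This is the cost of losing pairs to drop-out. It is not the gain from a mixed model, which recovers only part of that loss.

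**The case against.** The best defence is that the three schedules are nested. Aim 1 and the opening of section 9 are summaries, neither says that no other assessments are made, and every reading they list is contained in the Pain Assessments text. That text is itself in section 9, so staff who read the whole section would find session 10. Recruitment is planned at one institution. A reader might infer that different sites would run different schedules, but the documents give little support for that. This part stands: it is mainly an alignment edit.

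A second defence is that the analysis sentence has a natural reading: within-session change at the first and last sessions, plus change from before session 1 to after session 20. That is plausible, but it is not stated, it does not fit the two-assessment description at the opening of section 9, and it still leaves session 10 without a role.

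A reader might also infer that the plan throws the session-10 data away. It does not say so, and section 15 promises analysis of data collected up to discontinuation. The supportable statement is narrower: neither named test can use a subject without a last-session value in a first-to-last comparison, and no other method is given.

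Finally, this is a single-arm feasibility study with no power claim. That limits the consequence to an undefined estimand and lost information. No stated figure is wrong.

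**Conclusion.** The concern holds, and the plan should be changed. The schedule is described with 4, 2 and 6 readings, the pre and post readings are not named, and session 10 has no planned use. About 12 to 22 of 25 subjects would enter a first-to-last paired test, and between 0 and 12.5 others could have mid-course readings that the test cannot use.

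Two stronger readings are not supported. One is that session 10 would rescue some definite number of subjects. That number depends on when subjects leave, which is not given. The drop-out figure in section 10 also covers people who consent and then withdraw, some of whom may leave before any session, so zero is compatible with the documents. The other is that the completers' result is known to be biased. Bias arises only if leaving is related to pain response, and the documents do not say why subjects would leave.

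The counts assume full enrolment of 25. The detectable changes assume two-sided alpha 0.05 and 80% power.

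**What to change.** 1. Align Aim 1 and the opening of section 9 with the six-reading schedule in the Pain Assessments text.
2. For each repeated score, such as the VAS and the DALLAS scale, replace the across-course paired test with a linear mixed model on all available readings. Use session (1, 10, 20) by pre/post as categorical effects, a subject random effect and small-sample degrees of freedom.
3. Name the whole-course contrast in advance: after session 20 minus before session 1. This matches the onset and end assessments at the opening of section 9. Report before session 20 minus before session 1, and the within-session changes, separately.
4. Keep the Wilcoxon signed-rank test on completers as a sensitivity analysis.
5. Analyse the global change measure on its own, because perceived improvement has no baseline value.

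The cost is protocol and SAP wording. No assessments are added beyond those in the Pain Assessments text, although staff who had planned from Aim 1 would have to add session 10. The model assumes that missingness is explained by the observed scores, it relies on small-sample inference, and its session-10 readings help only for subjects who leave after session 10.

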**7. BACKGROUND AND SIGNIFICANCE**

Pain is one of the most common and debilitating symptoms of a wide range of injuries and diseases. Its treatment often relies on prescription or over-the-counter pharmaceutical medications such as Nonsteroidal anti-inflammatory drugs (NSAIDs), Acetaminophen, corticosteroids, antidepressants, anticonvulsants, and opioids. There are also non-pharmacological pain management methods such as transcutaneous electrical nerve stimulation (TENS), physical therapy, as well as alternative approaches including thermal, acupuncture, and meditation. Physicians typically iteratively explore these options as they strive to identify the most suitable methods for each patient. Unfortunately, one of the most commonly prescribed pain treatments, opioids, has a potential to lead to addiction, which has led to an epidemic of opioid over-prescription and abuse, with dangerous personal and societal consequences. This opioid crisis is a principal issue in public health with over 47,000 related annual deaths, as well as social and economic welfare costs of over \$78.5 billion a year in the USA. Safe and effective alternatives for treating pain that reduce dependence on opioids are, therefore, urgently needed to address this emergency.

Proposed Solution: This project proposes a non-invasive, non-pharmacological alternative that could treat pain

by combining an innovative electroencephalography (EEG)-based Neurofeedback (NF) solution in an immersive virtual reality (VR) environment. This combined NF-EEG-VR (NEVR) pain treatment system is designed to specifically address the underlying brain activity associated with perception of (or attention to) pain. In the scope of this project, we will initially focus our work on chronic low back pain (cLBP) as this is a growing segment of chronic pain sufferers with a 39% worldwide lifetime prevalence, and whose sufferers have historically been a heavy user population of opiates. In the Phase I SBIR study, NEVR will be validated on patients with chronic lower back pain of multifactorial etiology.

## 8. PROGRESS REPORT

None. This is a new study.

## 9. RESEARCH DESIGN AND METHODS

This will be a single arm clinical trial with up to 25 subjects undergoing NF training in VR using the NEVR prototype and protocol. This is a feasibility study where only one arm (NF group) is needed for demonstration of feasibility; the number of subjects is based on a recently published study by Mayaud et al. 2019.

Each patient will be recruited from [name] patient population, and after signing informed consent will undergo a cognitive and behavioral pain assessment followed by 20 NF sessions, every other day or 3 times per week. Each session will take up to 1 hour and will consist of: donning of NEVR system, recording EEG while subjects sit with their Eyes Open then Eyes Closed for EEG threshold calibration, followed by performing six 5-minute blocks of NF. Subjects will then be asked to conduct a brief usability survey after each session. At the end of the 20 sessions, subjects will undergo the same cognitive and behavioral assessment conducted at the study's onset.

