## **10. HUMAN SUBJECTS**

In order to meet the aims of the study, we will enroll up to 25 subjects that consent and complete all study procedures. Anticipating a standard 10-50% drop-out rate (consented and withdrawn or dropped out), the estimated accrual will be a maximum of 25 total subjects at all sites, depending on screen failures and drop out.

The plan is to recruit subjects UCSD, with a maximum enrollment of 25 subjects.

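### Feasibility is the only reason given for the single arm, yet no completion, attendance or retention rate is estimated, while uncontrolled pre/post tests are said to show treatment effects

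*Combined protocol and SAP*

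**What the plan says.** **Design.** Section 9 calls the trial a feasibility study and states that "only one arm (NF group) is needed for demonstration of feasibility". No other reason for omitting a comparator is given. On size, "the number of subjects is based on a recently published study"; no power, effect size or precision target is stated. The cap is 25 subjects in Sections 9 and 10, and Aim 1 in Section 6 speaks of 20.

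**Analysis.** The Statistical Analyses part of Section 9 plans:
- change in alpha activity from the first to the last recording, correlated with clinical outcomes;
- a search for the smallest set of electrodes that detects alpha reliably;
- paired t-tests or Wilcoxon signed-rank tests of the pain assessments before and after treatment, "to determine the effects of the treatment";
- tabulation and analysis of the usability surveys, to guide the Phase II device.

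**Drop-out.** Section 10 sets accrual "Anticipating a standard 10-50% drop-out rate", counted from consent. The figure is used for planning only and is not an outcome.

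**Selection.** The inclusion criteria in Section 10 require a pain score above 6 out of 10.

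**The concern.** The stated purpose and the inferential analysis do not match. Feasibility carries the whole case for a single arm, but the plan does not say what would be measured to show it, in which subjects, or what value would suffice. Whether patients in substantial pain will attend 20 sessions of up to an hour each is a central open question for this programme, and no planned analysis answers it.

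The formal tests are instead aimed at a treatment effect, which the case for one arm does not cover. Subjects enter because their pain is high, so some fall is expected from regression to the mean alone. Expectation, the passage of time and repeated staff contact add to it. The tests also need last-session data, so subjects who leave early drop out of them. With heavy loss, a favourable pain p-value could come from about half the cohort, with no planned statement that the other half left.

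**Working it through.** **1. Stated purpose against planned output**

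| Feasibility question | Planned analysis (Section 9) | Criterion |
|---|---|---|
| Can fewer electrodes serve? | Electrode-subset analysis | None; reliability not quantified |
| Is the system usable? | Survey tabulated and analysed | None; no summary measure |
| Do subjects complete 20 sessions? | None | None |
| How many sessions are attended? | None | None |
| Is there a treatment effect? | Paired t or Wilcoxon tests | Not a feasibility question; no comparator |

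**2. The plan's own figures.** No sample-size calculation is given, so none can be reproduced. Applying the Section 10 drop-out range to the cap of 25 (assuming all 25 consent and are eligible):
- 10% drop-out: 25 × 0.90 = 22.5 expected completers.
- 50% drop-out: 25 × 0.50 = 12.5 expected completers.

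The probability that at least 20 of 25 complete is 0.967 at 90% retention, 0.617 at 80%, 0.194 at 70% and 0.002 at 50%. The anticipated range therefore runs from near-full completion to half the cohort lost.

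**3. Precision available.** Exact (Clopper-Pearson) 95% limits for x completers of n: the lower limit is the 2.5% quantile of Beta(x, n − x + 1), and the upper is the 97.5% quantile of Beta(x + 1, n − x).

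| Completers | Proportion | Exact 95% CI |
|---|---|---|
| 13/25 | 52% | 31.3-72.2% |
| 20/25 | 80% | 59.3-93.2% |
| 22/25 | 88% | 68.8-97.5% |
| 16/20 | 80% | 56.3-94.3% |

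Even the intervals near the two ends of the drop-out range overlap slightly, from 68.8% to 72.2%.

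**4. What a threshold could do.** The rule is to declare feasibility if at least r of n complete. One-sided error is P(X ≥ r) under a completion rate p0 judged too low; power is P(X ≥ r) under a satisfactory rate p1; X is binomial. The documents give no such rates, so these are assumed. Each r is the smallest with error at most 0.05.

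| n | p0 | p1 | r | Error | Power |
|---|---|---|---|---|---|
| 25 | 50% | 80% | 18 | 0.022 | 0.891 |
| 25 | 60% | 90% | 20 | 0.029 | 0.967 |
| 25 | 70% | 90% | 22 | 0.033 | 0.764 |
| 25 | 60% | 80% | 20 | 0.029 | 0.617 |
| 20 | 50% | 80% | 15 | 0.021 | 0.804 |
| 20 | 60% | 80% | 17 | 0.016 | 0.411 |

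Rates 30 points apart can be separated with 25 subjects. Rates 20 points apart cannot be separated reliably.

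**The case against.** **The plan is not empty on feasibility.** A reader might infer that it contains efficacy tests only and can conclude nothing about its purpose. The documents do not support that. The electrode-subset and usability analyses are feasibility-type outputs that serve Aim 2 directly, and the surveys are to be analysed as well as tabulated. Completion could also be counted afterwards. This stands. What remains is that neither analysis has a criterion, neither shows whether 20 sessions can be delivered, and a threshold chosen after the count is seen does not demonstrate feasibility.

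**Phase II.** A reader might infer that the Phase II decision would rest on the pain tests. No section says so. The inputs that Section 6 names for the Phase II design are the electrode analysis and user feedback, and no decision rule appears.

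**The drop-out range cannot be applied to session 1 starters.** This stands. Section 10 counts from consent, and 25 is a cap that also depends on screen failures. The main denominator should start at consent, and the intervals above are illustrations.

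**A usable-EEG proportion.** It is tempting to add one based on the impedance and artifact check. Under the NF Protocol part of Section 9, that check must be passed before recording starts, so the proportion would be near 100% by construction and would say nothing about signal quality during the training blocks.

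**Stable co-treatment.** Subjects agree to make no drug adjustments and have no added interventional therapies. This limits one rival explanation, by self-report, but does not deal with regression to the mean, expectation or time.

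**Conclusion.** The point holds in a limited form. Feasibility is the sole justification for one arm but is not defined, and completion, attendance and retention are not estimated. The inferential outcome tests address a treatment effect that the design cannot isolate. Followed as written, the plan could attribute pain change to treatment without support and leave unstated how many subjects could be taken through 20 sessions.

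The gap matters because the anticipated drop-out spans about 13 to 22 completers if 25 enter. The planned size can support a prespecified criterion if the unacceptable and satisfactory rates are about 30 points apart (power 0.89 for 50% against 80%), but not if they are close (0.62 for 60% against 80%). These figures assume 25 in the denominator and rates chosen for illustration; with 20 subjects they are weaker.

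The size of any regression to the mean cannot be computed, since no variability is given and the documents do not say whether the qualifying pain score also serves as baseline. This should be changed before enrolment; it does not make the trial uninformative.

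**What to change.** In the Statistical Analyses part of Section 9:

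1. Make the primary result the proportion of all consented, eligible subjects who complete 20 sessions, with an exact 95% CI. Show the same proportion among those who start session 1, and report the number of sessions attended.
2. State before enrolment the completion rate that will count as feasible. Give the error and power of the rule at the planned number, and note that up to 25 subjects separates only widely spaced rates.
3. Replace "to determine the effects of the treatment" with *describe pre/post change*. Report pain changes as exploratory estimates with CIs and the number of subjects contributing data, and state that they cannot be attributed to treatment.

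The cost is mainly wording: no added subjects, visits or arm. Visits completed must be known in any case for the prorated payments in Section 20. The downside is that the pain p-values lose confirmatory status, and the sponsor must commit to a completion threshold in advance.
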